### **3.5.2.2. Time to Recovery of Platelets**

For patients who respond, time to recovery of platelets for each cycle will be defined as the date of first dose of study treatment to the date that the platelets recover to counts of 50,000/ $\mu$ l after each cycle. During each cycle, the nadir will be calculated. Recovery is not considered to have occurred until after the date of this nadir. Also, patients are required to be platelet transfusion independent on the date of recovery. Platelet transfusion independence will be defined as no platelet transfusion for at least 7 days prior to the assessment. If the nadir equals or exceeds the target level of recovery, the date of recovery is defined as the first date after the final dose in the cycle on which the target level was reached and the patient was transfusion independent. Patients not achieving the target levels of platelet recovery are censored at the last laboratory evaluation prior to the next cycle, first follow-up anti-cancer treatment, or death, whichever comes first.

## **4. ANALYSIS SETS**

Data for all subjects will be assessed to determine if subjects meet the criteria for inclusion in each analysis population prior to releasing the database and classifications will be documented per standard operating procedures.

### **4.1. Full Analysis Set**

The full analysis set will include all enrolled patients, and will be the primary analysis set for evaluating all efficacy endpoints and patient characteristics.

### **4.2. Per Protocol Analysis Set**

Not applicable.

### **4.3. Safety Analysis Set**

The safety analysis set will include all enrolled patients who receive at least 1 dose of study medication. The safety analysis set will be the primary analysis set for evaluating treatment administration/compliance and safety.

## 4.4. Other Analysis Sets

### 4.4.1. QTc Analysis Set

The QTc analysis set will include patients in the safety analysis set who have a baseline ECG and at least one post-dose ECG.

### 4.4.2. PK Analysis Sets

All patients who are treated with GO and contribute at least one PK sample will be included in the PK analysis set.

#### 4.4.2.1. Concentration Analysis Set

The PK concentration analysis set is defined as all enrolled patients who received at least 1 dose of GO and have at least one PK concentration.

#### 4.4.2.2. Parameter Analysis Set

The PK parameter analysis set is defined as all enrolled patients who received at least 1 dose of GO and who have at least one PK parameter.

CCI

### 4.4.4. Immunogenecity Analysis Set

The immunogenicity analysis set include patients in the safety analysis set who have at least 1 immunogenicity sample with results.

## 5. GENERAL METHODOLOGY AND CONVENTIONS

The final primary analysis will be performed at the study subject data set release after LSLV. No other reporting events are planned. If deemed agreeable to Pfizer and/or regulatory authorities, reporting for the adult cohort may be performed at study subject data set release after the LSLV for adult patients, and separately, reporting for the pediatric cohort may be performed at study subject data set release after the LSLV for pediatric patients.

### 5.1. Hypotheses and Decision Rules

The primary QTc analysis will be based on a non-inferiority hypothesis testing framework. If the upper bounds of one-sided 95% confidence intervals of change from baseline in QT measurements using Fridericia's heart rate correction for adult patients for each of the QTc

sampling time points (Day 4, 0 hours, and Day 7, at 0, 2, 4 and 6 hours) from Cycle 1 are below 20 msec, the post dose QTc interval will be considered to be “non-inferior” to the baseline; the QTc effect of GO will be concluded to be not unacceptable.

Thus with an overall 1-sided significance level of 0.05 and a non-inferiority margin of 20 msec, assuming a standard deviation of 18.8 msec and a mean change from baseline for QTcF up to 10 msec, 50 adult patients will provide 90 % power for assessing the 5 QTc sampling timepoints using paired difference in means with the t distribution. **CCI**

The inclusion of 6 additional pediatric patients ( $12 \leq \text{age} \leq 17$  years) was determined based on agreement with CHMP.

## 5.2. General Methods

Summary tables will have separate tabulations (columns) for adult and pediatric patients, and also a total column combining adult and pediatric patients. If adult and pediatric patients are to be reported at different times, for example if adult LPLV is reached while pediatric enrollment is still ongoing, with pediatric patients to be reported at a later database release then summary tables may not contain a total column. Data will be pooled across sites and countries.

### 5.2.1. Nominal Timepoints

For data where visit labels are specified on the CRF, then these labels will be used for all algorithms and analyses as the nominal timepoint. Where visit labels are not specified on the CRF such as data captured on log pages, data will be assigned to cycles; refer to Section 5.2.5 for further detail. Unplanned records may also be assigned to visits according to dates.

ECG parameters: Only the scheduled ECGs will be used in the primary analysis, and only the specific Cycle 1 timepoints of Day 4, 0 hours, and Day 7, at 0, 2, 4 and 6 hours for adult patients will be assessed for interpretation of study results. The nominal timepoints are Screening, Cycle 1 Day 1 at 0, 1, 2, 4 hours; Day 4 at 0, 2 hours; Day 7 at 0, 2, 4, 6; and Cycle 2 Day 1 at 0, 2 hours; Day 7 at 0, 2, 6. As noted in Section 3.4, the Screening and Cycle 1 Day 1 at 0 hours timepoints will be considered in the determination of the baseline value based on the dates.

Response: Response by investigator is assessed after each cycle. These nominal timepoints (Cycle 1 and Cycle 2) will be used in reporting.

**CCI**

### **5.2.2. Unscheduled Assessments**

ECG parameters: Only the scheduled ECGs will be used in the primary analyses. Interval measurements from unscheduled ECGs will be included in some of the categorical analyses, refer to Section 5.2.8.4 for further details.

### **5.2.3. Definition of Study Day**

The study day for assessments occurring on or after the first dose of study treatment (e.g., adverse event start date) will be calculated as:

Study day = Date of the assessment/event - start date of study treatment + 1.

The study day for assessments occurring prior to the first dose of study treatment (e.g., baseline characteristics, medical history) will be negative and calculated as:

Study day = Date of the assessment/event –start date of study treatment.

The study day will be displayed in all relevant data listings.

### **5.2.4. Definition of Cycle and Cycle Day**

For Cycle 1 and Cycle 2 the actual start date for each patient will be determined from the first start date of dosing from the respective CRF exposure page with a dose recorded.

If Cycle 2 is administered, then the actual stop date for Cycle 1 will be calculated as the start date of Cycle 2 minus one day.

For the last Cycle, actual stop date will be calculated as the minimum of the last dose + 36 and the start date of subsequent anticancer therapy.

The cycle day will be calculated as Cycle day = Date of the assessment/event – cycle start date + 1.

The cycle day will be displayed in all relevant data listings.

### **5.2.5. Assignment to Cycles**

Data collected in log pages, such as adverse events, and laboratory results, will be assigned to cycles. Cycles are defined in Section 5.2.4. For adverse events, the assignment will be based on the start date. Adverse events that start after the end of the last cycle will be assigned to a cycle called Follow-up.

### **5.2.6. Date of Last Contact**

The date of last contact will be derived for patients not known to have died using the latest complete date (i.e. imputed dates will not be used in the derivation) among the following:

- All patient assessment dates including local laboratory assessment dates, vital signs, performance status, ECG, bone marrow assessments, extramedullary disease assessment),
- Start and stop dates of concomitant therapies including non-drug treatments or procedures, including transfusions,
- Start and end dates of anti-cancer treatments administered after study treatment discontinuation including systemic therapy, radiation, and HSCT,
- AE start and end dates,
- Last date of contact collected on the ‘Survival Follow-up’ CRF (do not use date of survival follow-up assessment unless status is ‘alive’),
- Study treatment start and end dates,
- Enrollment date, and
- Date of discontinuation on disposition CRF pages (do not use if reason for discontinuation is lost to follow-up or death).

### **5.2.7. Standard Derivations and Reporting Conventions**

The following conversion factors will be used to convert days into weeks, months or years:  
1 week = 7 days, 1 month = 30.4375 days, 1 year = 365.25 days.

Percentages will be reported to one decimal place. The rounding will be performed to closest integer / first decimal using the common mid-point between the two consecutive values. E.g., 5.1 to 5.4 will be rounded to an integer of 5, and 5.5 to 5.9 will be rounded to an integer of 6.

Duration calculations such as Overall Survival (defined in Section 3.2.4) will be reported in months will use +1 thus OS = ((death date or censoring date) – start date +1)/ 30.4375.

### **5.2.8. ECG Derivation Details**

#### **5.2.8.1. Corrected QT interval derivation**

$$\text{Fridericia's heart rate correction: } \frac{QT}{\sqrt[3]{60/HeartRate}}$$

$$\text{Bazzett's heart rate correction: } \frac{QT}{\sqrt{60/HeartRate}}$$

The ECG core laboratory (vendor) will provide the corrected QT intervals according to the Fridericia’s and Bazzett’s corrections.

A study specific correction for adult patients will be derived as  $QT/(RR)^S$  where S is determined as follows:

The study specific QT correction factor (ICH E14 Step 4, May 12, 2005) will be derived for adult patients in the QTc analysis set using the individual replicates from the selected baseline (baseline is defined in Section 3.4) QT and RR.

No study specific QT correction factor will be assessed for the 6 pediatric patients.

Prior to estimating the regression, QT and RR will be transformed by the natural logarithm to  $\ln(QT)$  and  $\ln(RR)$ , respectively.  $\ln(RR)$  will be treated in the regression as the explanatory variable with  $\ln(QT)$  as the response variable. The regression equation will be as follows:

$$\ln(QT) = \text{Intercept} + S \times \ln(RR) + \text{Error}$$

Where S = slope of the regression line.

Once (S) is estimated, it will be used to derive the study specific QT correction, QTcS, for adult patients in the QTc analysis set.

#### **5.2.8.2. Averaging of triplicate ECG parameter measurements**

After the above variables have been derived within each patient and scheduled timepoint, each ECG parameter (including QTcF, QTcB, QTcS, QT, HR, PR, RR, QRS) should each be averaged as follows:  $(1^{\text{st}} \text{ measurement} + 2^{\text{nd}} \text{ measurement} + 3^{\text{rd}} \text{ measurement}) / 3$ . All summary statistics, analyses and figures will be based on the triplicate averaged data from the ECG core laboratory.

#### **5.2.8.3. Change from baseline**

The change from baseline calculations for ECG parameter measurements is derived from the triplicate averaged measurements. Change from baseline is defined as a patient's parameter value at a particular timepoint minus baseline value (value - baseline value). Change from baseline calculations should only use post-dose ECG measurements at the scheduled nominal timepoints (Day 1 at 1, 2, 4 hours; Day 4 at 0, 2 hours; Day 7 at 0, 2, 4, 6 for Cycle 1; and in Cycle 2 Day 1 at 0, 2 hours; Day 7 at 0, 2 6 hours). Baseline is defined in Section 3.4.

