2. STUDY OBJECTIVES AND ENDPOINTS

Primary Objective:	Primary Endpoint:

 To assess the effect of GO on the QTc interval. 	
 Maximum change from baseline in corrected QT interval (QTc).
Secondary Objectives:	Secondary Endpoints:

 To characterize the PK of single-agent GO following the fractionated regimen (ie, 3 mg/m² on Days 1, 4, and 7). To assess the safety of GO with fractionated dosing of 3 mg/m². To assess the immunogenicity of GO. To assess response and overall survival. 	
 PK parameters: clearance and volume of distribution. Adverse events (AEs) and abnormal laboratory findings. Incidence of anti-drug antibody (ADA)/neutralizing antibodies (NAb). Response: complete remission (CR) and complete remission with incomplete hematologic recovery (CRi) achieved after GO. Overall Survival.

CC1

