9.3.1. Analysis of Primary Endpoint

ECG measurements from the ECG core laboratory (an average of the triplicate measurements) will be used for the statistical analysis and all data presentations. Only the scheduled ECGs will be used in the primary analysis. The last available planned triplicate measurements prior to first dose will be used as baseline.

QT measurements will be corrected by heart rate (QTc) including Bazzett's (QTcB) and Fridericia's (QTcF) methods, and a study-specific correction method (QTcS) will be evaluated according to the observed data. QTcF will be used for the primary analysis.

The absolute corrected QT interval and changes in QTc (QTcB, QTcF, and/or QTcS) from baseline will be summarized using descriptive statistics by nominal time point.

A random effect model with the nominal timepoints as a fixed effect and patients as a random effect will be used for the primary analysis to estimate the mean change in QTcF (primary endpoint) at the post baseline nominal timepoints (Day 4, 0 hours, and Day 7, at 0, 2, 4 and 6 hours) along with 2-sided 90% confidence interval for the mean. The maximum increase in QTc from baseline will be computed over all time points. The maximum increase from baseline will be summarized with descriptive statistics.

Categorical analysis of changes in QTc (QTcB, QTcF, and/or QTcS) from baseline including absolute QTc interval prolongation and maximum increase will be provided. Interval measurements from unscheduled ECGs will be included in the categorical analyses.

Baseline versus worst on treatment QTc according to maximum CTCAE grade will be summarized using a shift table.

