		The high level summary of AEs was updated, and summary tables of AE that had actions taken due to the AE were added. Additional summaries were added for in-text tables.	The update is consistent with current standard tables and oncology reporting conventions. Updates to AE summaries were made to facilitate production of in-text CSR tables consistent with recently updated oncology conventions.
		A summary of AESI of INFUSION RELATED REACTIONS by ADA status was added.	The summary was added to assess the impact of ADA on safety.
		Laboratory summaries were changed from worst (maximum) grade to shift from baseline tables; similarly non-CTC graded laboratory summaries were changed to shift, and summary of liver function tests was added.	Updates to summaries were made to facilitate production of in-text CSR tables and consistent with recently updated oncology conventions.
		ECG maximum increase from baseline as a continuous variable summarized with descriptive statistics was removed.	It was considered sufficient to summarize this categorically.

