#### **5.2.8.4. Categorization of ECG parameters**

The categorization of QTc will be per ICH E14 guidance:

The absolute QTc interval (QTcF and QTcS) value for each patient will be categorized as  $\leq 450$ ;  $> 450 - \leq 480$ ,  $> 480 - \leq 500$ ;  $> 500$  msec, using the maximum value post baseline (considering both cycles) based on the averaged triplicate values. Similarly, the absolute values of HR, PR and QRS will be categorized as follows: HR  $\leq 50$  bpm, HR  $\geq 120$  bpm, PR  $\geq 220$  msec and QRS  $\geq 120$  msec.

The maximum increase from baseline QTc will be categorized as:  $\leq 30$  msec,  $> 30 - \leq 60$  msec and  $> 60$  msec based on the averaged triplicate values. Similarly, the maximum increase from baseline for HR will be categorized as  $\geq 20$  bpm and maximum increase from baseline for PR will be categorized as  $\geq 20$  msec.

CCI

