#### **6.6.5.5. Maximum increase from baseline QTc**

Categorical analysis of maximum increase from baseline in QTc (QTcF and/or QTcS) and will be summarized. . As described in Section 5.2.8.4, the categories of  $\leq 30$  msec,  $>30 - \leq 60$  msec and  $>60$  msec will be used and the number and percentage of patients in each category will be summarized. A similar categorical analysis of HR and PR will be provided (HR increase from baseline  $\geq 20$  bpm and PR increase from baseline  $\geq 20$  msec).

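### The SAP drops unscheduled ECGs from the maximum QTc increase table (>30, >60 msec), which the protocol says includes them, and its cross-reference leads to no rule

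*SAP*

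**What the plan says.** **Protocol.** Section 9.3.1 describes categorical analyses of QTc change, "including absolute QTc interval prolongation and maximum increase will be provided". The next sentence is unqualified: "Interval measurements from unscheduled ECGs will be included in the categorical analyses". The same section keeps the primary analysis on scheduled ECGs. Section 7.1.1 calls for triplicate ECGs when a patient has a cardiac or neurologic adverse event (it names syncope, dizziness, seizures and stroke) and sends all ECGs to the core laboratory.

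**SAP.** Section 5.2.2 narrows the protocol's sentence: "Interval measurements from unscheduled ECGs will be included in some of the categorical analyses, refer to Section 5.2.8.4 for further details". Section 5.2.8.3 then states: "Change from baseline calculations should only use post-dose ECG measurements at the scheduled nominal timepoints", and lists those timepoints. Section 5.2.8.4 gives the cut-offs. For absolute QTc the basis is the "maximum value post baseline (considering both cycles) based on the averaged triplicate values"; for maximum increase the categories are up to 30, above 30 to 60, and above 60 msec, again on triplicate averages. Section 6.6.5.5, which specifies the maximum-increase table, refers back to 5.2.8.4. The one place that expressly uses unscheduled ECGs is the CTCAE shift table in 6.6.5.4.

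The SAP version history adds: "ECG maximum increase from baseline as a continuous variable summarized with descriptive statistics was removed". The reason given is that the categorical summary was thought sufficient.

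**The concern.** A programmer following the SAP must leave unscheduled ECGs out of a table in which the protocol puts them. Nothing in the SAP marks this as a decision or gives a reason.

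The ECGs lost include those taken because something happened to the patient. ECGs are scheduled only at screening and on dosing days, so after Cycle 1 Day 7 a patient who does not go on to Cycle 2 has no further scheduled tracing. From then on, only an unscheduled ECG can show a large increase.

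The table also carries more weight than it did. Protocol Section 2 lists the maximum change from baseline in QTc as the primary endpoint, and with the continuous summary removed, the categorical table is the only per-patient summary of that quantity. A report of no patient above 60 msec could then mean only that no scheduled ECG showed such a rise.

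**Working it through.** The plan states no figure on this point, so the check is mainly a comparison of the texts, followed by some arithmetic for scale.

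**1. Does the SAP rule reach this table?**
- Protocol 9.3.1: maximum increase is one of the categorical analyses, and unscheduled ECGs enter those analyses without exception.
- SAP 5.2.8.3: change from baseline uses scheduled nominal timepoints only.
- SAP 5.2.8.4 and 6.6.5.5: maximum increase is a change from baseline, and neither section exempts it.
- SAP 5.2.8.2: averages are formed within scheduled timepoints. The maximum-increase categories use averages, so this blocks unscheduled ECGs a second time.
- SAP 5.3.5: no average is computed unless all three replicates exist, and the rule is written for scheduled assessments.

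The exclusion therefore follows from the text. For the absolute-value table (>450, >480, >500 msec), 5.2.8.3 does not apply; there the omission is implied by 5.2.8.2, not stated.

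**2. Does the 5.2.2 pointer lead to a rule?** The visible text of 5.2.8.4 does not mention unscheduled ECGs. A redaction follows it, but the SAP contents list runs from 5.2.8.4 through a redaction to 5.2.10. The hidden text is thus most likely Section 5.2.9, though a hidden rule cannot be fully excluded.

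**3. How much time has no scheduled ECG?** (inputs: SAP 5.2.8.3 and 3.5)
- Cycle 1 post-dose timepoints: Day 1 at 1, 2, 4 h (3) + Day 4 at 0, 2 h (2) + Day 7 at 0, 2, 4, 6 h (4) = 9, on 3 days. Cycle 2 adds 2 + 3 = 5, on 2 days.
- One cycle: active monitoring ends at the latest on Day 7 + 36 = Day 43.
- Days without a scheduled ECG: 43 − 3 = 40, and 40/43 = 93%. The figure is lower if subsequent therapy starts earlier.

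**4. Can the absolute categories stand in?** The lowest category is 450 msec or less, and 450 − 60 = 390. A patient with a baseline below 390 msec can rise by more than 60 msec and stay in it. Hypothetical example: 385 to 448 msec is a rise of 63 msec, still in the lowest category.

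**5. What would one missed case do?** Assume all 50 adults are in the table; Clopper-Pearson 95% intervals:
- 0/50 = 0% (0 to 7.1%)
- 1/50 = 2.0% (0.05 to 10.6%)
- 2/50 = 4.0% (0.5 to 13.7%)

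Each missed case moves the proportion by 2.0 percentage points.

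**6. Is the primary analysis touched?** No. Both documents restrict it to scheduled ECGs. The stated 90% power also reproduces: the noncentrality is (20 − 10)/(18.8/√50) = 3.76; a one-sided 0.05 t test with 49 df has power 0.980 at each timepoint; five timepoints treated as independent give 0.980^5, which is 0.906 before rounding. It does not depend on this point.

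**The case against.** **The SAP may modify the protocol.** Both documents say so; only major changes to the primary endpoint or its analysis also need a protocol amendment. The word some in SAP 5.2.2 could be a deliberate narrowing. It could even be read as exempting one or both tables in 5.2.8.4 from 5.2.8.3. The latitude is real. But the SAP names no exempted table, and the version history neither lists nor explains a narrowing. A text that supports both readings still needs correcting.

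**The primary-endpoint argument is weaker than it looks.** Protocol 9.3.1 attaches that label to the mean change in QTcF, and SAP 3.1.1 defines the endpoint as change from baseline. This stands: the mismatch is a separate issue, and the non-inferiority conclusion does not rest on this table.

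**Such cases appear elsewhere.** SAP 6.6.5.3 gives the largest change at each nominal timepoint; the shift table in 6.6.5.4 uses unscheduled replicates; protocol 8.2.2 makes an abnormal finding with symptoms an adverse event, which can fall under the cardiac conduction grouping in SAP Appendix 2. This reduces the risk of losing a case altogether. However, the first source covers scheduled timepoints only and is not per patient, the second classifies absolute values, and the adverse event tables do not give the size of the increase.

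**The 93% counts calendar days, not risk.** Protocol 1.2.2.3 reports near-total antibody clearance within 14 days (at 9 mg/m², a higher dose). On that basis Days 22 to 43, which are 22 of the 40 days, come after clearance; the other 18 do not. The figure describes ECG coverage and says nothing about expected events.

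**Core-laboratory readings may be incomplete.** Protocol 7.1.1 sends all ECGs to the core laboratory but also speaks of keeping documentation of clinically indicated ECGs at the site. Single unscheduled tracings may therefore be less well covered than event triplicates.

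**Conclusion.** The concern holds. As written, the SAP excludes unscheduled ECGs from the maximum-increase table, the protocol includes them, and the cross-reference meant to settle the matter does not. For the absolute-value table the same gap is implied only.

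The effect is confined to outlier reporting. The primary model, the 20 msec margin and the power are unchanged. The number of increases missed is unknown, because the documents give neither an expected number of unscheduled ECGs nor a baseline QTc distribution; the 1/50 versus 0/50 contrast is for scale only. The conclusion assumes that the redaction after 5.2.8.4 hides no rule on unscheduled ECGs, and that the core laboratory has read the event-triggered triplicates, as protocol 7.1.1 directs. The point should be corrected because the omitted ECGs are tied to clinical events and no other per-patient summary of maximum increase remains.

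**What to change.** Amend SAP 5.2.8.3, 5.2.8.4, 6.6.5.4 and 6.6.5.5 as follows:

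- Take maximum post-baseline QTc and maximum increase, for the categorical tables, over scheduled and unscheduled core-laboratory ECGs. Exempt these tables from the scheduled-only rule and keep that rule for the primary model.
- State how unscheduled ECGs are averaged, including sets with fewer than three tracings.
- State the window in which they count, for example the active safety monitoring period. The on-treatment period in SAP 3.5 runs to the end of follow-up and would admit ECGs taken long after treatment.
- Correct the pointer in 5.2.2 so that it also leads to 6.6.5.4.
- Show scheduled-only counts beside the combined counts.

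If the omission is intended, name the tables that leave unscheduled ECGs out and record this as a departure from protocol 9.3.1, with the reason.

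The cost is SAP wording and table programming, with no new data collection provided the core laboratory holds the readings; this should be confirmed first. Outlier counts may rise slightly, unscheduled ECGs are not taken equally often in all patients, and later tracings may reflect concurrent illness or other medicines. The side-by-side columns make this visible.
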